11.5.1.2 Safety data for the ongoing studies OC5-OL-01, OC5-DB-02 and OC5-OL-02

The current OC5-OL-01 study started in May 2014 and is ongoing in Germany. Fourteen subjects were screened and 12 subjects have been enrolled in the study and received study drug. This study includes late-stage patients with ESRD who are on dialysis. Most of these patients are on a waiting list for transplantation. Eight subjects continued into the continued treatment phase of the study, and one subject currently remains in the study (as of September 2019). There have been no severe nor serious related AEs for Oxabact® in this ongoing study.

In the ongoing, double-blind OC5-DB-02 study in patients with retained but reduced kidney function (eGFR <90ml/hr/1.73m²), 16 patients have been randomised. There have been 8 SAEs reported to-date; none of them was considered related to study drug. There have been no reported SAEs in the ongoing open-label OC5-OL-02 study (currently 4 enrolled patients).

Overall, the safety data accrued to date would suggest that the OC5 drug product is safe and well tolerated and appears to have a similar safety profile as the earlier OC3 drug product. Further safety information of the OC5-OL-01, OC5-DB-02 and OC5-OL-02 studies has been detailed in the current version of the Oxabact® Investigator's Brochure.

11.5.2 Systemic infections due to *O. formigenes*

O. formigenes is a commensal bacterium in the intestinal tract and is a strict anaerobe. Following an extensive search of the literature, there have been no reports of local or systemic infections where *O. formigenes* have been isolated. Preparations of *O. formigenes* have been administered to rats, pigs and humans without any apparent toxicity or side effects including local or systemic infections. In the completed clinical studies, no patient experienced any infection due to *O. formigenes*.

Any patient who develops signs and symptoms of bacteremia requiring hospitalisation should be evaluated to identify the source of infection (e.g., lung, GI tract, meningeal, etc.). Evaluation for the source of bacterial infection should include clinical and laboratory tests and cultures for common pathogens. Empiric antibiotic treatment should include coverage for common pathogens. It is recommended that an Infectious Diseases Specialist be consulted to assist in the assessment and management of the patient.

O. formigenes has shown sensitivity to chloramphenicol, doxycycline, erythromycin, and tetracycline. In the event of unexpected infection caused by the study medication erythromycin is the recommended first line antibiotic therapy in children and adults, and tetracycline is the recommended second line antibiotic therapy in older children and adults. If common pathogens have been excluded or if the infection is not

responding to erythromycin or tetracycline the study medication should be stopped until further evaluation.

11.5.3 Elevated levels of plasma formate

Since *Oxalobacter formigenes* converts oxalate to formate, there may be the possibility of elevated plasma formate levels following administration of high doses of OC5. Formate is a metabolite of methanol responsible for the toxicity observed with methanol poisoning. Typically, toxic effects require prolonged exposure to elevated plasma formate levels.

Previous studies with Oxabact® (including OC2, OC3 and OC5) in over 100 patients with doses ranging from NLT 10⁷ to NLT 10⁹ CFU have not indicated any signs or symptoms of elevated formate plasma levels, metabolic acidosis or methanol poisoning. The main manifestations of methanol poisoning are metabolic acidosis and ocular toxicity. Any patient who develops signs and symptoms of metabolic acidosis should be evaluated to identify the source (e.g. evaluation of serum bicarbonate, blood pH, anion gap, osmolality gap and plasma formate).

Formate accumulation in plasma is the main reason for acidosis in early, uncomplicated stages of metabolic acidosis.¹⁴ Metabolic acidosis is characterised by low blood pH (arterial pH < 7.38 or venous pH < 7.34) or low levels of serum bicarbonate, HCO₃⁻ (< 18 mmol/L). Decreased levels of serum bicarbonate or blood pH will serve as an indication of elevated levels of formate. The OC5-OL-01 study will investigate these early signs of elevated plasma formate as part of routine safety labs. Low levels of serum bicarbonate or blood pH should trigger determination of the anion gap and the osmotic gap in order to confirm or rule out the diagnosis of metabolic acidosis due to elevated formate levels.

If metabolic acidosis is diagnosed, the acidosis should be corrected as quickly as possible and therapy provided, if appropriate. If a diagnosis due to elevated formate levels cannot be excluded or if the metabolic acidosis cannot be corrected by standard of care the study medication should be stopped until further evaluation. Further evaluation should then include levels of plasma formate and visual disturbance test.

11.6 Laboratory safety measurements

The laboratory safety tests include:

- Haematology: Complete Blood Count (CBC) with differential and platelet count.
- Chemistry: Blood Urea Nitrogen (BUN), creatinine, electrolytes (Na⁺, K⁺, Mg⁺⁺, Ca⁺⁺, HCO₃⁻, Cl⁻), glucose, pH, albumin, alkaline phosphatase, ALT, AST, total bilirubin, and total protein.
- Random Urine (Urinalysis): protein, glucose, pH.

Laboratory parameters from haematology, chemistry and urinalysis will be assessed at the local laboratory at each clinic. Laboratory safety tests will be performed as specified in Table 4: Schedule of assessments – the first 14 weeks of the study, Table 5: Schedule of assessments – continued treatment Year 1 and 2 and Table 6: Schedule of assessments – continued treatment Year 3.

12 STATISTICS

12.1 Statistical methods

Efficacy: The primary endpoint, change in total plasma oxalate from baseline, will be evaluated over time for each patient. Evidence for efficacy will be provided as the combined evaluation of individual case studies. Plasma oxalate levels will be measured on a monthly basis throughout the first 24 months of the continued treatment period and once every 3-4 months during the last 12 months of the continued treatment period. All secondary endpoints will be analysed using the same methodology.

For the primary endpoint the change in total plasma oxalate levels will be based on the average from two baseline measurements (week 2 and week 4) and one measurement every 4th week throughout the first 24 months of the continued treatment period and every 3-4 months during the last 12 months of the continued treatment period.

The change in plasma oxalate during 4 weeks follow-up period after the end of the 6 weeks treatment period with OC5, will be based on one measurement at week 10 and one measurement at week 14. The last observation will be carried forward in case of missing values at week 14 and/or week 10.

Two interim analyses will be performed: The first analysis will be based on patients who complete the first year of continued treatment. The second interim analysis will be based on all study data obtained up to 24 months. Both interim analyses will evaluate all captured efficacy and safety parameters.

The individual changes in plasma oxalate per week will also be calculated as an average slope using regression of plasma oxalate by week.

The study involves a small number of patients and natural history data on changes in total and free plasma oxalate for this population is limited. Response to treatment is likely to vary depending on the baseline plasma oxalate level, individual hepatic oxalate production and age of each patient. Accordingly, the sample size is not based on assumptions of efficacy outcome and statistical power, and the definition of analysis populations is not applicable. Any inferences from the data will be based on clinical relevance rather than statistical significance.

Safety: The safety will be summarised using descriptive statistics based on frequency, seriousness and severity of treatment emergent AEs. Clinically relevant changes in safety laboratory parameters will also be summarised.

All statistical analyses will be further defined in a Statistical Analysis Plan.

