Prior to enrollment patients will be on a stable dialysis regimen. This could be only haemodialysis (HD), only peritoneal dialysis (PD) or combined HD and PD. The choice of dialysis regimen will be decided upon by the investigator and individualised to remove adequate oxalate to minimise the risk for systemic oxalosis. The PD regimen (number of days/week, hours per treatment, volume of dialysis buffer) and HD regimen (number of days/week; hours per treatment; blood and dialysate flow rates; and HD membrane) will be maintained for the duration of the study. This will be monitored and recorded by measuring volume of spent dialysate from HD and PD and quantifying dialysis dose of each HD session in terms of Kt/V measurement using an online clearance monitor. Each patient's dry weight (target bodyweight after the dialysis session) will also be recorded.

The total plasma oxalate (the primary end point of this study) will be measured at weeks 2, 4, 6, 8, 10, 12, 14, thereafter monthly for the first 24 months of continued treatment and every third or fourth month during the last 12 months of the continued treatment period (Figure 6 and Figure 7). A blood sample will be obtained after two consecutive days of completed dialysis regimen the preceding days, but prior to the dialysis session on the day of sampling. The plasma samples will be processed at each clinical site and analysed for total plasma oxalate at the Academic Medical Center, Amsterdam and for free plasma oxalate at the local lab (Bonn University Clinical laboratory).

Speckle Tracking Echocardiography and traditional echocardiography will be performed, if possible, at screening visit (+/- 1 month) or before start of continued treatment period (at visit week 14). Speckle Tracking Echocardiography and traditional echocardiography will then be repeated at week 24 in the continued treatment period and thereafter every 6 months until end of treatment, if possible.

Figure 6: Study design for OC5-OL-01 - the first 14 weeks of the study.

	Screening (0-4 weeks)		Baseline (4 weeks)		Treatment (6 weeks)						Post-trtm (4 weeks)				
Week	0	1	2	3	4	5	6	7	8	9	10	11	12	13	14 ²
Clinic visit	X	X	X	X	X	X	X	X	X	X	X	X	X	X	X
Plasma oxalate	X		X	X	X	X	X	X	X	X	X	X	X	X	X
Stool	X	X	X	X	X	X	X	X	X	X	X	X	X	X	X
Safety labs	X	X	X	X	X	X	X	X	X	X	X	X	X	X	X
STE	X ²	:				:					:				

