3 PATIENTS FOR ANALYSIS

3.1 Analysis populations

3.1.1 Full-Analysis-Set (FAS)

The FAS includes all patients who have received at least one dose of the investigational drug. This population will be used as primary analysis population for the analysis of efficacy.

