6.6 Statistical analysis primary and secondary endpoints

6.6.1 Primary endpoint

The primary endpoint is change in total plasma oxalate level during OC5 treatment, compared to the baseline value. All primary endpoint analyses will be performed for the FAS as primary

analysis, and for the mFAS as post-hoc analysis. All primary endpoint analyses will be done on the overall treatment period, unless otherwise specified.

Summary statistics of the measurements will be presented on a per-visit basis. Both the actual value as well as the change from baseline value will be presented.

Summary statistics tables will also be presented for patients on hemodialysis only and for patients on peritoneal dialysis only separately, if there are more than 3 subjects in any of the groups. In case of less than 3 patients for one of the groups, the separation will not be made, and the summary statistics not presented.

To visualize the effects through time graphically, the following plots will be created:

- Mean +/- SE and individual plots will be created to visualize the course of total plasma oxalate values through time. Both the actual values as well as change from baseline values will be presented. These plots will be created for the overall treatment period as well as the continued treatment period (including the baseline value).
- Combined spaghetti plots will be created using the actual values, for the overall treatment period and the continued treatment period. No spaghetti plots will be created for change from baseline.

Taking into consideration the limited sample size, in addition, a mixed-effect repeated measures model (MRMM) may be performed on the change from baseline values using baseline total plasma oxalate and week as the independent variables. If the assumption of normality is violated, a log transformation will be applied first (and a back transformation will be done on the results). SAS PROC MIXED (with the REML default) will be used for the analysis. The basic SAS code will be as follows.

```
proc mixed data=...;  
  class usubjid;  
  model change= time baseline;  
  repeated time / subject=usubjid type=...;  
run;
```

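### Protocol 12.1 specifies the primary endpoint without on-drug weeks 6, 8 and 10, the SAP specifies it more widely, and SAP section 7 does not record the difference

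*Protocol*

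**What the plan says.** Protocol 12.1 has one sentence stating what the primary change is built from: "based on the average from two baseline measurements (week 2 and week 4) and one measurement every 4th week throughout the first 24 months". Those months are counted within CT, and the sentence then adds only the sparser samples of the final CT year. Weeks 6, 8 and 10 of the first course are not in it. The following paragraph uses week 10 only for the off-treatment change to week 14. The section also says that defining analysis populations does not apply.

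Other parts of the protocol are wider. Section 6.1 states: "The total plasma oxalate (the primary end point of this study) will be measured at weeks 2, 4, 6, 8, 10, 12, 14", followed by the CT visits. Section 10 defines the endpoint as change while on OC5 against the average of the baseline values, with no limit to CT. The synopsis statistics text mentions the initial part of the study as well as CT.

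The SAP is wider too. Of the full analysis set (FAS, anyone who took a dose), SAP 3.1.1 says: "This population will be used as primary analysis population for the analysis of efficacy". SAP 6.6.1 adds: "All primary endpoint analyses will be done on the overall treatment period, unless otherwise specified". SAP 3.1.2 and 6.6.1 give the modified set (mFAS, patients dosed in CT) a post-hoc role. SAP 1 says that the plan agrees with protocol version 12. SAP section 7, which lists changes from the protocol, does not mention this one.

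On numbers, Protocol 11.5.1.2 reports: "Fourteen subjects were screened and 12 subjects have been enrolled in the study and received study drug", and "Eight subjects continued into the continued treatment phase of the study".

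**The concern.** The two documents point to different samples, and in effect different patients, for the same primary endpoint. Under the 12.1 sentence, only patients who entered CT can have a post-baseline value. Those are the patients whom the SAP treats as a post-hoc set.

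The difference is not neutral. Protocol 6.1 offers CT only when the responsible investigator believes that the drug has had a positive effect. In an open-label study without a control arm, a result confined to continuers is conditioned on apparent response. Weeks 6, 8 and 10 are the only on-drug samples taken before that selection.

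A report could cite either definition as pre-stated. The SAP version also needs tightening, because its analysis period is not tied to a list of visits.

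**Working it through.** The plan states no count of patients or samples behind the primary endpoint, and no power or SD. There is no plan figure to reproduce, so the check is a comparison and a count.

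**Definitions side by side**

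| Source | Post-baseline samples | Patients who can have a value |
|---|---|---|
| Protocol 12.1, primary-endpoint sentence | CT visits | CT entrants |
| Protocol 6.1 | Weeks 6 to 14 and CT visits | All treated |
| Protocol 10 | Any on-OC5 sample | All treated |
| SAP 3.1.1, 5.1, 6.6.1 | Overall treatment period | All treated (FAS) |
| SAP 3.1.2, 6.6.1 | Same, post-hoc | CT entrants (mFAS) |

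**Inputs**

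- Treated: 12. Entered CT: 8 (Protocol 11.5.1.2).
- First-course on-drug samples per patient: 3, at weeks 6, 8 and 10 (Protocol 6.2.3, Table 4).
- Off-drug samples per patient in the first 14 weeks: 2, at weeks 12 and 14 (Protocol 6.2.4).

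**Patients without a value under the 12.1 sentence**

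12 − 8 = 4, and 4/12 = 33.3%.

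**On-drug samples that the sentence does not name**

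3 × 12 = 36 scheduled, of which 3 × 4 = 12 belong to the four who did not continue. These are ceilings, since a missed visit or early withdrawal lowers them.

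**Off-drug samples that the SAP period may include**

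The SAP abbreviation list expands TRT as the overall treatment period, but SAP 2.2 uses TRT for the initial 14-week phase. Both readings cover weeks 6, 8 and 10 for every treated patient. Neither clearly excludes weeks 12 and 14. If these are included, the first 14 weeks hold (3 + 2) × 12 = 60 scheduled post-baseline samples. Of these, 2 × 12 = 24 (40%) are off drug. For the four non-continuers, that 40% applies to all their post-baseline samples. Per-visit tables keep the weeks apart, but the mixed model and the individual slopes in SAP 6.6.1 pool across them. The CT week 0 sample raises the same issue: it is taken as treatment restarts, and that visit may coincide with week 14.

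**Baseline**

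Protocol 12.1 measures CT visits against the week 2/4 average. SAP 6.1 keeps that as the primary baseline but adds week 14 as a baseline for CT-phase analyses. One CT sample can therefore have two change values.

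**How much selection could matter (illustration with assumed inputs)**

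Assume normally distributed early changes and that the 8 continuers were the best 8 of 12. Simulation (200,000 runs) puts their mean early change 0.51 SD better than the mean of all 12. If r is the correlation between early and later change, the carry-over to later change is r × 0.51 SD:

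| r | Carry-over (SD) |
|---|---|
| 0 | 0 |
| 0.3 | 0.15 |
| 0.5 | 0.25 |
| 0.7 | 0.36 |
| 1 | 0.51 |

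**The case against.** A reader might infer that the protocol excludes the first-course samples, so that four patients contribute nothing and the primary analysis will be run on eight. The documents do not support that. The 12.1 sentence omits those weeks but never limits the endpoint to CT visits. The same section promises evaluation over time for each patient, and its slope regression is not confined to CT. It also leaves further definition of the analyses to the SAP, which names all treated patients as the primary population. The four still provide baseline and safety data and, if sampled, the week 10 to 14 change.

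The stakes are also limited. SAP 6.1 rules out formal significance testing, and the protocol rests inference on clinical relevance. Individual plots and listings will show every sample, and FAS and mFAS results are both planned. A protocol change needs ethics and regulatory approval (Protocol 19), and one patient remained in the study in September 2019.

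All of this stands, and it is why the point is not critical. It does not remove the discrepancy. The 12.1 sentence is the only one in the protocol that says which samples the primary change rests on. The SAP claims agreement with that version and departs from it without saying so. In a descriptive study, the choice of samples, baseline and patients is most of the pre-specification.

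**Conclusion.** The inconsistency is real. Read literally, the 12.1 sentence leaves 4 of 12 treated patients (33%) without a post-baseline primary value and leaves up to 36 scheduled on-drug samples unnamed. The remaining 8 were offered CT on a judged positive effect. If the SAP is followed, no samples are lost. The harm is two primary definitions that could each be cited, one of them selected on apparent response, plus an overall treatment period loose enough to admit off-drug weeks 12 and 14.

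The four is derived from 12 and 8, not stated. The documents do not say why those patients did not continue, so the 0 to 0.51 SD range shows what selection could do and is not an estimate of bias. Severity: should-fix, not must-fix.

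**What to change.** 1. In SAP 5.1 and 6.6.1, list the on-treatment samples for the primary endpoint: weeks 6, 8 and 10, plus CT visits after treatment restarts. Leave out weeks 12 and 14 and the pre-restart CT week 0 sample. Express each as change from the week 2/4 average.
2. Label change from the week 14 baseline (SAP 6.1) as supplementary.
3. Report two labelled parts: the first-course result in all treated patients, and the CT result in continuers, described as selected on judged effect.
4. Use one meaning for TRT and for the overall treatment period throughout the SAP.
5. Record the departure from Protocol 12.1 in SAP section 7. Correct 12.1 at the next amendment if there is one; this point alone does not need one.

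The cost is a small amount of rewording and re-tabulation. No new data are needed.

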13 DIRECT ACCESS TO SOURCE DATA/DOCUMENTS

The investigator/institution should permit study-related monitoring, audits, IEC review and regulatory inspections, and should provide direct access to the source data/medical record.

The monitor should verify that each patient has consented in writing to direct access to the original medical record/source data (by the use of written patient information and signed informed consent). During the monitoring, the data recorded in the CRFs by the investigator will be checked for consistency with the source documents/medical record by the study monitor (source data verification). Any discrepancies of data should be documented and explained in the monitoring reports.

For every patient, the medical records should include the minimum following information:

- patient number and study id
- date for information given, signing informed consent, screening
- treatments given, including investigational product(s)
- visits to the clinic
- AE/SAE, if any
- concomitant medication
- time and reason for discontinuation, if any

There are data that are recorded only on the CRF, which are associated with protocol-specific procedures and not with normal clinical care practice. For such clinical data the investigator would not be expected to duplicate the information. Source data location will then be specified in the Investigator file.

14 QUALITY CONTROL AND QUALITY ASSURANCE

14.1 Monitoring and audits

Monitoring of the study will be arranged by the sponsor according to GCP guidelines. Monitoring visits will be performed regularly to the study sites during the study, to ensure that all aspects of the protocol are followed. Source documents will be reviewed for verification of consistency with data recorded on the Case Report Forms and product accountability will be performed as a part of the monitoring visits.

The study site may also be subject to quality assurance audits by the sponsor as well as inspection by the appropriate regulatory agencies.

It is important that the investigator and their relevant personnel are available during the monitoring visits and possible audits/inspections, that study related records are made available, and that sufficient time is devoted to the monitoring process.

14.2 Site personnel

Investigators and other key personnel shall provide curriculum vitae or equivalent, that will confirm their suitability for the clinical study. All investigators and key personnel

should be listed together with their responsibilities in the study on a signature and delegation log.

It is the responsibility of the Investigator to ensure that all personnel involved in the study are fully informed of all relevant aspects of the study, including detailed knowledge of and training in all procedures to be followed.

